6.1.1.3.2 RESPONSE EVALUATION AFTER A COMPLETE RESECTION

A complete resection will be defined as contiguous contrast-enhancement <10 mm in 2 perpendicular measurements in each of 2 perpendicular planes (i.e., axial and coronal). Because neither the RECIST[80] nor MacDonald [81] criteria are completely appropriate for patients with minimal residual disease, a modified version of these criteria will be used as outlined below.

6.1.1.3.2.1 COMPLETE RESPONSE

Complete disappearance of enhancing tumor on consecutive CT or MRI images at least 1 month apart, and neurologically stable or improved and at the same or a lower steroid dose. To be assigned a status of “Complete Response” as a best overall response, changes in tumor measurements must be confirmed by repeat assessments that should be performed no less than 4 weeks after the criteria for response is first met.

6.1.1.3.2.2 PARTIAL RESPONSE

Partial response is not assessable in patients without sufficient measurable disease.

6.1.1.3.2.3 STABLE DISEASE

Insufficient change to qualify for Complete Response or Progressive disease.

6.1.1.3.2.4 PROGRESSIVE DISEASE

At least a 25% increase in the longest diameter on an axial image of any enhancing tumor on consecutive CT or MRI images with a minimum of ≥ 5 mm of contiguous contrast-enhancement in 2 perpendicular measurements in each of 2 perpendicular planes (i.e., axial and coronal).

6.1.1.3.2.5 NOT ASSESSABLE

Progression has not been documented and one or more sites have not been assessed.

6.1.1.3.2.6 POST-TREATMENT EVALUATION

After treatment termination the patient will be seen at an outpatient clinic for one additional visit within 30 days +/- 7 days. Physical and neurological examination, blood tests (CBC and Biochemistry panel) will be performed during this visit. Patient mortality and adverse events will be documented on the case report forms.

After the post treatment follow up visits, if the patient has not progressed by treatment termination, patient will have contrast-enhanced brain MRI every 3 +/- 1 months for 12 months. Then MRIs every 6 +/- 2 months for 24 months, then yearly +/- 1 month thereafter or until disease progression, whichever comes first.

In case of clinical progression an MRI will be performed within 21 days. After the end of study therapy visit post disease progression, the patient will not be required to return to the clinic for follow-up but will be followed until death by telephone every 3 months to monitor their status.

6.1.2 Dosing and Administration

6.1.2.1 Adjuvant Temozolomide Treatment

All patients will receive adjuvant temozolomide.

6.1.2.2 Adjuvant Phase Cycle 1:

Four to six weeks after completing the temozolomide + RT phase, the temozolomide is administered for an additional 12 cycles of adjuvant treatment. Dosage in Cycle 1 (adjuvant) is 150 mg/m² once daily for 5 days followed by 23 days without treatment.

6.1.2.3 Adjuvant Cycles 2-12:

At the start of Cycle 2, the dose is escalated to 200 mg/m², if the CTC non-hematologic toxicity for Cycle 1 is Grade ≤2 (except for alopecia, nausea and vomiting), absolute neutrophil count (ANC) is ≥ 1.5 x 10⁹/L, and the platelet count is ≥ 100 x 10⁹/L.

The dose remains at 200 mg/m² per day for the first 5 days of each subsequent cycle unless toxicity occurs. If the dose was not escalated at Cycle 2, escalation should not be done in subsequent cycles.

6.1.2.4 Temozolomide Dose Reduction or Discontinuation

Dose reductions during the adjuvant phase should be applied according to Tables 7 and 8 below. Cycle 1 Day 1 should not start until the ANC is above 1.5 x 10⁹/L (1,500/μL) and the platelet count exceeds 100 x 10⁹/L (100,000/μL). If unable to start within the Cycle 1 start window, the patient will be considered a screen fail.

The next cycle of temozolomide should not be started until the ANC and platelet count exceed these levels. Dose reductions during the next cycle should be based on the lowest blood counts and worst non-hematologic toxicity during the previous cycle. Dose reductions or discontinuations during the adjuvant phase should be applied according to Tables 7 and 8. Routine blood monitoring should be conducted in accordance with local site procedures.

TABLE 7. TEMOZOLOMIDE DOSE LEVELS FOR ADJUVANT TREATMENT

Dose Level	Dose (mg/m ² /day)	Remarks
-1	100	Reduction for prior toxicity
0	150	Dose during Cycle 1
1	200	Dose during Cycles 2-12 in absence of toxicity

TABLE 8. TEMOZOLOMIDE DOSE REDUCTION OR DISCONTINUATION DURING ADJUVANT TREATMENT

Toxicity	Reduce temozolomide by 1 Dose Level ^a	Discontinue temozolomide
Absolute Neutrophil Count	<1.0 x 10 ⁹ /L	See footnote b
Platelet Count	<50 x 10 ⁹ /L	See footnote b
CTC Non-hematological Toxicity (except for alopecia, nausea, vomiting)	CTC Grade 3	See footnote b

^a: temozolomide dose levels are listed in table 7.

^b: temozolomide is to be discontinued if dose reduction to <100 mg/m² is required or if the same Grade 3 non-hematological toxicity (except for alopecia, nausea, vomiting) recurs after dose reduction.

CTC = Common Toxicity Criteria.

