
4) Optune therapy should start within two weeks of start of adjuvant temozolomide, but not more than 7 weeks from the end of temozolomide/RT and will be continuous throughout study. Compliance documentation will be obtained every 4 weeks +/- 7 days.
							

5) Every 3 months until death. The only data required during survival follow-up is DOD.
							

6) Biochemistry panel will include electrolytes, creatinine, bilirubin, liver enzymes.
							

7) Patients will begin treatment with temozolomide at 4 weeks (+14 days) from end of radiotherapy. Cycle 1 will be dosed at 150mg/m² daily for 5 consecutive days of a 28-day cycle.
							

Study Procedure:	Screening ≤14 days prior to Day 0	Day 0 : Begin TMZ Treatment	Week 4 (-3/+7 days) and every 4 weeks until treatment stop	Week 8 (±7 days) and every 8 weeks only until treatment stop	Progression	After Treatment Stop (Week 4 (+/- 7 days) from end of treatment)	Survival follow-up

8) Patients will begin treatment with temozolomide Cycle 2 and subsequent cycles every 4 weeks (-3/+7 days) at 200mg/m² PO daily for 5 consecutive days, if CTC hematologic toxicity for cycle 1 is grade < 1 and the CTC non-hematologic toxicity for cycle 1 is grade ≤ 2. If dose escalation is not appropriate, the dose should remain at 150 mg/m² PO daily for 5 consecutive days for Cycle 2 and onward.
							

9) Verification of tissue availability and location should be determined at screening visit. When available, formalin fixed and paraffin embedded (FFPE), pathology slides and/or frozen samples will be obtained for primary tumors and first recurrent tumors.
							

10) Labs to be completed within 3 days for pre-TMZ cycles. Screening and other labs are within the visit windows noted. Pregnancy Test required for WOCBP only at Screening.
							

11) DICOM images will be shipped to Beth Israel Deaconess Medical Center for electric field mapping analysis at baseline, first progression and second progression. Imaging performed between shipping time points should be included in the next shipment.
							

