6 STUDY INTERVENTION

6.1 Study Intervention(s) Administration

6.1.1 Study Intervention Description

6.1.1.1 Treatment Plans – Optune (TTFIELDS) + temozolomide

Patients will begin study treatment with temozolomide and TTFIELDS within 2 weeks of the baseline evaluation, and no later than 6 weeks from last dose of concomitant temozolomide or radiation therapy (the latter of the two). A minimum of 6 and a maximum of 12 cycles of adjuvant temozolomide will be given, depending on tolerability and toxicity.

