6.1.2.6 Optune (TTFIELDS) + temozolomide

Optune treatment will be initiated in an outpatient clinic by the investigator's team at each center or at home by Novocure's device support specialists (DSS). 3D mapping of tumors using the FDA-approved NovoTAL software will be completed by a NovoTAL-certified treating physician or by Novocure. Scalp shaving, array placement and all device support services (including patients' and families' education of device operation, downloading and processing of technical and compliance data, and troubleshooting device malfunction) will be provided by the DSS for the first placement. Patients and/or their caregivers will continue treatment at home after being trained in device use with the support of DSS as needed.

TTFIELDS will start within 2 weeks of the first cycle of adjuvant temozolomide but must be within 7 weeks after end of temozolomide/RT. Adjuvant Temozolomide will continue for a minimum of 6 and a maximum of 12 cycles. Optune will continue for a maximum of 2 years. At first progression, patients will be allowed to continue with TTFIELDS therapy with any other therapy per standard of care. Patients will receive up to 12 one-month courses of continuous Optune treatment together with standard adjuvant temozolomide. The decision to add each additional treatment course will depend on the lack of treatment related serious adverse events which reappear upon re-challenge and lack of clinical disease progression. All technical aspects of the Optune device are handled by the DSS.

During Optune treatment the patient will be permitted to interrupt treatment for personal needs with the goal of achieving approximately 75% of the time over each 4-week period. Compliance reports with TTFIELDS will be obtained by Novocure's DSS per usual clinical treatment procedures. If a patient's compliance is below 75% of the time over any 4-week period, the patient will be trained on the importance of compliance and any barriers to compliance will be addressed by the DSS. If a patient's compliance is below 50% of the time over any 4-week period, the patient will be trained on the importance of compliance and any barriers to compliance will be addressed by the DSS and study staff.

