7 STUDY INTERVENTION DISCONTINUATION AND PARTICIPANT DISCONTINUATION/WITHDRAWAL

7.1 Discontinuation of Study Intervention

Discontinuation from study treatment does not mean discontinuation from the study, and remaining study procedures should be completed as indicated by the study protocol. If a clinically significant finding is identified (including, but not limited to changes from baseline) after enrollment, the investigator or qualified designee will determine if any change in participant management is needed.

Any serious adverse event deemed life threatening by the treating physician that is definitely related to the study device will be cause for immediate cessation of treatment for the patient. Patient follow up will continue after such an event.

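### Table 8 states no temozolomide action for a first on-treatment Grade 4 non-haematological toxicity, and schedule note 8 conflicts with Tables 7 and 8 after a Cycle 1 Grade 3 event

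*Combined protocol and SAP*

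**What the plan says.** Section 6.1.2.4 gives the governing rule: "Dose reductions or discontinuations during the adjuvant phase should be applied according to Tables 7 and 8". It also sets the basis for the next dose: "Dose reductions during the next cycle should be based on the lowest blood counts and worst non-hematologic toxicity during the previous cycle".

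Table 7 has three dose levels: 100, 150 (Cycle 1) and 200 mg/m² per day. Table 8 lowers the dose by one level for a neutrophil count below 1.0 × 10⁹/L, for platelets below 50 × 10⁹/L, or for a non-haematological toxicity of Grade 3, with alopecia, nausea and vomiting excepted. For discontinuation every row points to footnote b: "temozolomide is to be discontinued if dose reduction to <100 mg/m² is required or if the same Grade 3 non-hematological toxicity", which must recur after a reduction.

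Note 8 to the Schedule of Activities (section 1.3) covers escalation at Cycle 2 and adds: "If dose escalation is not appropriate, the dose should remain at 150 mg/m² PO daily for 5 consecutive days for Cycle 2 and onward". It does not mention Table 8.

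Exclusion F(c) in section 5.2 lists Grade 4 non-haematological toxicity, with the same three exceptions, among baseline conditions that would prevent adjuvant temozolomide.

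**The concern.** A dose-modification table should give an action at least as strict for a worse toxicity as for a milder one. This one names a single grade, so the more severe event falls outside the stated trigger. The fallback severity scale in section 8.3.3.1 labels level 4 as life-threatening, so the missing case is the one where a clear instruction matters most.

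Note 8 adds a second problem. A site working from the schedule, and a site working from section 6.1.2.4, would give different Cycle 2 doses after the same Grade 3 event. What is at stake is patient safety and consistent dosing across the 10 to 20 centres named in the synopsis.

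**Working it through.** The plan states no figure to reproduce. The check is to apply the written rules case by case and then look for a rule elsewhere that fills the gap.

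**1. Table 8 applied at each Table 7 dose level (first event)**

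| Dose when the event occurs (mg/m²/day) | Grade 3, as written | Grade 4, as written | Grade 3 or 4, trigger changed to Grade ≥3 |
|---|---|---|---|
| 200 | 150 | none stated | 150 |
| 150 | 100 | none stated | 100 |
| 100 | stop (a dose below 100 would be needed) | none stated | stop |

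The three blank cells come from one omission. The haematological rows have no such gap, because a count below the threshold stays below it however low it falls.

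**2. Other places that might supply a Grade 4 action**

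- *Restart rule, 6.1.2.4*: "The next cycle of temozolomide should not be started until the ANC and platelet count exceed these levels". It refers to blood counts only.
- *Cycle 2 escalation, 6.1.2.3 and 8.1.2*: non-haematological toxicity above Grade 2 blocks the rise to 200 mg/m². No reduction or stop is given there.
- *Section 7.1*: the mandatory stop is for life-threatening events "definitely related to the study device will be cause for immediate cessation of treatment for the patient". Temozolomide toxicity is not covered.
- *Section 6.1.2.6*: "The decision to add each additional treatment course will depend on the lack of treatment related serious adverse events which reappear upon re-challenge". A first event is not covered.
- *Section 6.1.1.1*: "A minimum of 6 and a maximum of 12 cycles of adjuvant temozolomide will be given, depending on tolerability and toxicity". This gives no grade and no dose. Section 6.1.2.5 mentions discontinuation for toxicity, also without a trigger.
- *Section 7.2*: the investigator may withdraw a participant for an adverse event. This is a permission, not a dose rule.
- *Exclusion F(c)*: names Grade 4, but only at baseline.

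None of these states what to do with temozolomide after a first Grade 4 non-haematological event on treatment.

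**3. Note 8 against Tables 7 and 8, Grade 3 event in Cycle 1**

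- Tables 7 and 8: the Cycle 1 dose is 150, and one level down is 100 mg/m² per day.
- Note 8: escalation is not appropriate, so the dose stays at 150 mg/m² per day.
- Difference: 150 − 100 = 50 mg/m² per day for the same event.

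Sections 6.1.2.3 and 8.1.2 bar later escalation for such a patient but do not hold the dose at 150. The conflict therefore arises from the wording of note 8.

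**The case against.** The strongest reply is that no competent investigator would re-dose unchanged after a Grade 4 toxicity, and that the protocol supports that judgement. Next-cycle dosing rests on the worst toxicity, Table 7 describes 100 mg/m² as a reduction for earlier toxicity, and exclusion F(c) shows that the authors regard Grade 4 as incompatible with starting temozolomide. Section 7.2 allows withdrawal. SAEs reach the Coordinating Center within 24 hours and the Data Integrity and Safety Committee within 5 days (8.3.4.2), well inside a 28-day cycle. Sections 4.3.1, 6.2.2 and 6.2.4 refer to the package insert, and 6.2.4 has temozolomide given according to it. The insert may set a Grade 4 action, but its content is not in the documents. All of this stands and lowers the likely harm. It does not put an action into the table that sites are told to apply.

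A reader might infer three stronger points that the documents do not support:

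- *That the plan gives a higher dose after the worse event* (150 after Grade 4 against 100 after Grade 3, a ratio of 1.5). This requires Table 8 to govern Grade 3 while an escalation note governs Grade 4. If note 8 alone is followed, both get 150; if Grade 3 is read as a threshold, both get 100. The text does not select the first reading, and the worst-toxicity rule and F(c) point away from it.
- *That a Grade 3 toxicity recurring as Grade 4 is also left without a rule.* The wording of footnote b is narrow, but a sensible reader would count the worse recurrence as meeting it, and the re-challenge condition in 6.1.2.6 partly covers a serious one.
- *That the protocol already implies a permanent stop at Grade 4.* F(c) leans that way, but it is an entry criterion. Whether to reduce or stop on treatment is a clinical choice that the documents only partly settle.

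**Conclusion.** The point holds in a limited form. Table 8, read literally, has no action for a first on-treatment Grade 4 non-haematological event, and note 8 gives 150 mg/m² where Tables 7 and 8 give 100 mg/m² after a Cycle 1 Grade 3 event. Both follow from the wording alone.

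The practical size is low. The documents give no rate of Grade 4 toxicity, so the number of patients affected cannot be estimated, and the safeguards above make harmful re-dosing unlikely. No effect on overall survival, power or the SAE stopping boundaries is claimed. Whether the package insert already closes the gap is not assessed; if it does, what remains is that Table 8 does not say so. The correction is still worth making because it concerns a serious toxicity and costs very little.

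**What to change.** By amendment:

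1. In Table 8, change the non-haematological reduction trigger to *CTC Grade ≥3*.
2. In footnote b, refer to the same *Grade ≥3* non-haematological toxicity.
3. In schedule note 8, let the dose stay at 150 mg/m² *unless Table 8 requires reduction or discontinuation*.

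Instead of a one-level reduction at Grade 4, the sponsor may enter temozolomide-related Grade 4 toxicity in the Discontinue column. That would be in line with exclusion F(c), or with the package insert if it sets that action. Limiting the entry to related events keeps a disease-related event, such as the status epilepticus listed in 2.1.3.1.4.1, from ending temozolomide for good. Relatedness is already assessed for all adverse events (8.3.3.2), and chemotherapy-related SAEs must already be identified for the monitoring in 10.4.

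The cost is one table row, one footnote and one schedule note, with no extra visits, data or patients. The downside is that a few patients reduce or stop temozolomide earlier than the current wording requires. Under the simple trigger change these include some with unrelated Grade 4 events, as already happens at Grade 3 because Table 8 has no relatedness condition.

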6.1.2.5 Treatment after temozolomide discontinuation

Following temozolomide discontinuation due to toxicity or radiological disease progression (based on local interpretation of MRI), patients will be offered second line therapy for their disease. The following treatment options may be considered based on the patient's clinical condition per the treating physician's discretion:

1. Re-operation (TTFIELDS treatment will be interrupted for at least 2 weeks after reoperation or until wound healing is sufficient to resume).

2. Local radiation therapy
3. Second line therapy (at the discretion of the treating physician and not limited to traditional cytotoxic chemotherapy)
4. Combination of the above

TTF treatment will continue concomitant with second line treatments until second disease progression for TTFIELDS + temozolomide patients.

6.1.2.6 Optune (TTFIELDS) + temozolomide

Optune treatment will be initiated in an outpatient clinic by the investigator's team at each center or at home by Novocure's device support specialists (DSS). 3D mapping of tumors using the FDA-approved NovoTAL software will be completed by a NovoTAL-certified treating physician or by Novocure. Scalp shaving, array placement and all device support services (including patients' and families' education of device operation, downloading and processing of technical and compliance data, and troubleshooting device malfunction) will be provided by the DSS for the first placement. Patients and/or their caregivers will continue treatment at home after being trained in device use with the support of DSS as needed.

TTFIELDS will start within 2 weeks of the first cycle of adjuvant temozolomide but must be within 7 weeks after end of temozolomide/RT. Adjuvant Temozolomide will continue for a minimum of 6 and a maximum of 12 cycles. Optune will continue for a maximum of 2 years. At first progression, patients will be allowed to continue with TTFIELDS therapy with any other therapy per standard of care. Patients will receive up to 12 one-month courses of continuous Optune treatment together with standard adjuvant temozolomide. The decision to add each additional treatment course will depend on the lack of treatment related serious adverse events which reappear upon re-challenge and lack of clinical disease progression. All technical aspects of the Optune device are handled by the DSS.

During Optune treatment the patient will be permitted to interrupt treatment for personal needs with the goal of achieving approximately 75% of the time over each 4-week period. Compliance reports with TTFIELDS will be obtained by Novocure's DSS per usual clinical treatment procedures. If a patient's compliance is below 75% of the time over any 4-week period, the patient will be trained on the importance of compliance and any barriers to compliance will be addressed by the DSS. If a patient's compliance is below 50% of the time over any 4-week period, the patient will be trained on the importance of compliance and any barriers to compliance will be addressed by the DSS and study staff.

Approximately once per month, from baseline until treatment termination, all patients will report to an outpatient clinic where they will be assessed clinically and undergo routine laboratory examinations. The follow-up window for these visits is -3/+ 7 days for the Adjuvant TMZ follow-up window of approximately 12 months. The follow-up window after discontinuation of Adjuvant TMZ will be +/- 1 month. If patients are removed from study therapy due to toxicity and/or disease progression prior to the 2-year study treatment, the patients will have an end of study therapy visit within 1 month +/- 7 days. After this end of study therapy visit, patients will be followed by telephone interview every 3 months until death.

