1.3 Schedule of Activities (SoA)

TABLE 1: SCHEDULE OF ACTIVITIES: INTERVENTIONAL SUBJECTS

Study Procedure:	Screening ≤14 days prior to Day 0	Day 0 : Begin TMZ Treatment	Week 4 (-3/+7 days) and every 4 weeks until treatment stop	Week 8 (±7 days) and every 8 weeks only until treatment stop	Progression	After Treatment Stop (Week 4 (+/- 7 days) from end of treatment)	Survival follow-up
Informed Consent	X						
Medical History, Demographics	X						
Medication History	X						
MGMT methylation status	X						
Tumor Tissue Sample ⁹	X				X		
MRI of the brain ¹	X			X	X		
Physical Exam	X		X		X	X	
Neurological status, KPS	X		X		X	X	
CBC w/diff	X ¹⁰		X		X	X	
Pregnancy test (urine or serum)	X ¹⁰						
Biochemistry Panel ⁶	X ¹⁰		X		X	X	
Record Steroid Dose	X		X		X		
Quality of Life Questionnaires ²	X			X	X		
RANO	X			X	X		
Temozolomide Cycle		X ⁷	X ⁸				

Study Procedure:	Screening ≤14 days prior to Day 0	Day 0 : Begin TMZ Treatment	Week 4 (-3/+7 days) and every 4 weeks until treatment stop	Week 8 (±7 days) and every 8 weeks only until treatment stop	Progression	After Treatment Stop (Week 4 (+/- 7 days) from end of treatment)	Survival follow-up
Optune Therapy ⁴		X	X		X		
Optune Compliance ⁴			X				
Adverse Events		X	X	X	X	X	
Concomitant Medications		X	X	X	X	X	
Telephone Interview							X ⁵
DICOM Images shipped for electric fields mapping ¹¹		X			X		X

1) Screening MRI should be done within 21 days of study treatment start. MRI of the brain will be performed routinely at baseline and again every 8 weeks +/- 7 days until treatment termination or second progression, whichever is first. An MRI of the head will be obtained within 21 days in the event of clinical signs of progression. After the post-treatment follow up visit and the patient has not progressed by treatment termination, patient will have contrast-enhanced brain MRI every 3 +/- 1 months for 12 months, then every 6 +/- 2 months for 24 months, then yearly +/- 1 month thereafter or until disease progression, whichever comes first. All MRI scans should be performed with and without contrast and include the scalp.
							

2) Quality of Life will be measured using the EORTC QLQ-C30/BN20 and MMSE every 8 weeks +/- 7 days for the first 2 years then every 3 months thereafter.
							

3) Screening visit should occur within 14 days of adjuvant temozolomide start, with the exception of MRI which can be within 21 days (3 weeks) of adjuvant temozolomide start.
							

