8.3.5 Time Period and Frequency for Event Assessment and Follow-Up

The occurrence of an adverse event (AE) or serious adverse event (SAE) may come to the attention of study personnel during study visits and interviews of a study participant presenting for medical care, or upon review by a study monitor.

Any medical condition that is present at the time that the participant is screened will be considered as baseline and not reported as an AE. However, if the study participant's condition deteriorates at any time during the study, it will be recorded as an AE.

Changes in the severity of an AE will be documented to allow an assessment of the duration of the event at each level of severity to be performed. AEs characterized as intermittent require documentation of onset and duration of each episode.

Study Staff will record all reportable events with start dates occurring any time after the start of study treatment for 30 days after the After Treatment Stop Visit. At each study visit, the investigator or his/her designee will inquire about the occurrence of AE/SAEs since the last visit. Events will be followed for outcome information until resolution or stabilization.

During Survival Follow-up, AEs and SAEs will not be collected. Only Progression status and survival outcomes will be monitored during this stage of the study.

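### Follow-up of patients who stop for toxicity before progression is stated in conflicting ways; under one reading no progression date is collected and PFS may be scored at death

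*Combined protocol and SAP*

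**What the plan says.** The telephone rule in Section 6.1.2.6 begins "If patients are removed from study therapy due to toxicity and/or disease progression prior to the 2-year study treatment" and, after one end-of-therapy visit, continues "After this end of study therapy visit, patients will be followed by telephone interview every 3 months until death". It does not require that the patient has progressed, and it names no imaging. Table 1, footnote 5 (Section 1.3) says of this stage: "The only data required during survival follow-up is DOD". DOD is not in the abbreviation list; I read it as date of death.

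Other places differ:

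- Table 1, footnote 1: "After the post-treatment follow up visit and the patient has not progressed by treatment termination, patient will have contrast-enhanced brain MRI", at decreasing frequency until progression, with no exception for toxicity.
- Section 6.1.1.3.2.6 gives the same schedule: "if the patient has not progressed by treatment termination, patient will have contrast-enhanced brain MRI every 3 +/- 1 months for 12 months". It lifts clinic visits only for patients who have progressed: "After the end of study therapy visit post disease progression, the patient will not be required to return to the clinic for follow-up".
- Section 8.3.5, on survival follow-up: "Only Progression status and survival outcomes will be monitored during this stage of the study".
- Section 7.1: stopping treatment is not leaving the study, and "remaining study procedures should be completed as indicated by the study protocol".

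On the endpoint, Section 6.1.1.3.1.9 defines PFS as time to progression or death, whichever is first. Table 2 (Section 3) measures it to progression and does not name death. Section 10.2.1 specifies a log-rank test. No PFS censoring rule is given.

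**The concern.** A patient who stops study therapy for toxicity while progression-free falls under two sets of instructions. A site can follow Section 6.1.2.6 and footnote 5 to the letter and record nothing between the end-of-therapy visit and death. If the analysis then applies Section 6.1.1.3.1.9 literally, that patient's PFS time is the OS time.

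The telephone rule applies to interventional patients only. Control progression dates are taken from charts (Section 9.5), whatever the reason treatment stopped. The loss therefore lengthens PFS in the TTFields arm. PFS is a named secondary objective, and progression dates not collected during follow-up may be hard to recover later.

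**Working it through.** **1. The passages side by side, for a patient stopped for toxicity and not progressed**

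| Place | Imaging after stop | Progression recorded? |
|---|---|---|
| 6.1.2.6 | none named; telephone every 3 months | not stated |
| Table 1, footnote 5 | – | no, date of death only |
| Table 1, footnote 1 | MRI until progression | yes |
| 6.1.1.3.2.6 | MRI until progression | yes |
| 8.3.5 | none named | yes |

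Section 6.1.1.3.2.6 sits under a heading on complete resection. That does not remove the conflict, because footnote 1 repeats the schedule without that condition. Section 7.1 does not settle it either: it refers back to the procedures in the protocol, and those are what disagree.

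**2. How the record would be scored when progression is unseen and death is seen**

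- Section 6.1.1.3.1.9 read literally: event at death.
- Table 2 wording: no event; the censoring date is undefined.
- Censoring at last adequate assessment: censored near the stop.

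**3. Size**

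The plan gives no power, event count or alpha for PFS, so there is no PFS figure to reproduce. As a check on the design inputs, I recomputed one OS cell of Table 10 (90+0 controls, k = 2.0, 6 months' gain, stated power 0.894). HR = (22/28)² = 0.617. Expected events are 67.6 + 74.5 = 142.1, assuming historical entry spread over 40.6 months. Power = Φ(|ln 0.617| × √(142.1 × 0.25) − 1.645) = Φ(1.23) = 0.891, which agrees.

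Inputs to the PFS illustration:

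- From the plan: 90 v 90 patients; 36 months' accrual plus 24 months' follow-up; controls followed up to 60 months; OS median near 22 months; one-sided 0.05 (stated for OS, assumed here for PFS).
- Assumed: exponential PFS with median m of 6.7, 10 or 12 months, the same in both arms (6.7 is the TTFields-arm figure quoted for glioblastoma in Section 2.1.2.4); exponential post-progression survival with mean 0.75 × (22 − m)/ln 2; a share q of interventional patients assigned a toxicity stop, uniform over months 0–6 and effective only if before progression.

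Scoring an affected patient at death adds, on average and before administrative censoring, 0.75 × (22 − m)/ln 2 months: 16.6 for m = 6.7, 13.0 for m = 10 and 10.8 for m = 12.

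One-sided error from 4,000 null trials per cell, scored at death (censored at the stop in brackets):

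| PFS median | q = 0 | 5% | 10% | 20% |
|---|---|---|---|---|
| 6.7 | 0.050 | 0.104 (0.054) | 0.174 (0.057) | 0.374 (0.054) |
| 10 | 0.051 | 0.078 (0.052) | 0.117 (0.052) | 0.228 (0.046) |
| 12 | 0.044 | 0.078 (0.042) | 0.104 (0.054) | 0.169 (0.050) |

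At m = 10 the median observed PFS time in the interventional arm moves from 10.1 to 10.8 months with 10% stops and to 11.7 with 20%.

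Repeat runs over the same PFS medians, with a 2% case added, give 0.05–0.07 at 2%, 0.07–0.11 at 5%, 0.10–0.19 at 10% and 0.16–0.40 at 20%. Two variations show the sensitivity to the model:

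- Stops spread over months 1–12, with three assumed PFS–OS models: 0.09–0.18 at 10% (HR 0.89–0.96) and 0.15–0.41 at 20% (HR 0.81–0.91).
- The plan's Weibull OS (k = 2, median 22), with PFS an assumed fraction of OS and stops at months 1–12: 0.19–0.24 at 10% and 0.39–0.51 at 20%.

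**The case against.** Most of the protocol points to continued assessment. Footnote 1 and Section 6.1.1.3.2.6 make no exception for toxicity, Section 7.1 keeps patients in the study, and Section 8.3.5 retains progression status. Section 6.1.2.6 does not say that MRI stops, so calls and scans could run together. This stands as a reason to expect many sites to keep assessing. It does not remove footnote 5, which contradicts Section 8.3.5 outright.

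The stop rates have no support in the documents. Section 6.1.2.6.1 says temozolomide toxicity need not end Optune, and Section 2.1.3.1.1 expects no serious device effects. The 25% in Section 10.4 is a maximum acceptable rate of device-related SAEs, not a forecast of stops. This stands: the low-rate rows may be the relevant ones.

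A reader might infer that the plan makes PFS equal to time to death for these patients. The documents do not go that far: Table 2 words PFS as time to progression, and no rule says how a patient with missing assessments is handled. A reader might also infer that the arm comparison is certain to favour TTFields. That is not established, because chart review follows no protocol imaging schedule and can miss control progressions too.

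Finally, censoring holds the error near 0.05 only because stopping in the simulation is unrelated to prognosis. Section 6.1.2.6.1 also stops Optune for clinical deterioration, so real stopping may be informative.

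**Conclusion.** The contradiction is in the current text and leaves a route by which progression goes unrecorded for interventional patients who stop for toxicity before progression. The effect on PFS needs three things together: a site that follows Section 6.1.2.6 with footnote 5, an analysis that applies Section 6.1.1.3.1.9 without censoring, and enough such patients to matter. At 2% stops the effect is negligible. At 10% the error is roughly two to four times nominal, and at 20% roughly three to eight times, in the main set of runs; the Weibull variant goes higher. These figures rest on assumed stop rates, PFS medians and PFS–OS dependence, and show order of magnitude only.

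The primary OS analysis is not touched. This is worth correcting because the repair is cheap; it does not put the trial's main conclusion in doubt.

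**What to change.** 1. Reconcile Table 1 footnotes 1 and 5 with Sections 6.1.1.3.2.6, 6.1.2.6 and 8.3.5, so that they give one instruction for patients who stop before progression. Which imaging schedule applies is for the sponsor and investigators to decide.
2. Correct footnote 5 so that progression status and date are collected at each survival contact until first progression, as Section 8.3.5 already implies.
3. Align the PFS definitions in Table 2 and Section 6.1.1.3.1.9.
4. State in Section 10.2.1 that patients without further progression assessment are censored at their last adequate assessment. Add a sensitivity analysis that counts death as the event, because stopping may be related to prognosis.

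Cost: wording, one item in the survival telephone script if it is not already there (Section 8.2.2 refers to the script, but it is not in the documents), and one sensitivity analysis. Sample size does not change.
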